### 3.6.3 Additional safety assessments

#### 3.6.3.1 Laboratory variables, vital signs, and electrocardiograms (ECGs)

The following laboratory variables, vital signs, and electrocardiogram (ECG) variables will be analyzed. They will be converted into standard international units and conventional units (as appropriate).

- Hematology
  - Red blood cells (RBC), platelets: red blood cell count, hemoglobin, hematocrit, mean corpuscular volume (MCV), mean corpuscular hemoglobin (MCH), mean corpuscular hemoglobin concentration (MCHC), RBC Morphology, Reticulocyte, Mean platelet volume (MPV), platelet count (efficacy endpoint),
  - Coagulation: prothrombin time, International Normalized Ratio (INR), thrombin time, activated partial thromboplastin time (aPTT), fibrinogen,
  - White blood cells: white blood cell count, neutrophils, lymphocytes, monocytes, basophils, eosinophils
- Clinical chemistry:
  - Metabolism: glucose, total protein, albumin, creatine phosphokinase (screening only),
  - Electrolytes: sodium, potassium, chloride, calcium, phosphorus,
  - Renal function: creatinine, urea (blood urea nitrogen), creatinine clearance (Cockcroft and Gault method) (screening only, for adult participants), estimated glomerular filtration rate (eGFR) (Schwartz method) (screening only, for pediatric participants)
  - Liver function: alanine aminotransferase (ALT), aspartate aminotransferase (AST), alkaline phosphatase, total bilirubin, direct bilirubin and indirect bilirubin
- Urinalysis: pH, specific gravity, protein, glucose, ketones, bilirubin, blood, nitrites, urobilinogen, and leukocytes
- Immunoglobulin Levels: immunoglobulin G (IgG), immunoglobulin G Subclass 1 (IgG1), immunoglobulin G Subclass 4 (IgG4), immunoglobulin M (IgM), immunoglobulin E (IgE)
- Hemolysis panel: direct Coombs (anti-human globulin), haptoglobin

- Thrombopoietin (TPO)
- T-lymphocytes/ B-lymphocytes/natural killers (T/B/NK) counts:
  - CD3+ T Lymphocytes (Absolute), %CD3+ among lymphocytes
  - CD3+CD4+ T Lymphocytes (Absolute), %CD3+CD4+ among lymphocytes
  - CD3+CD8+ T Lymphocytes (Absolute), %CD3+CD8+ among lymphocytes,
  - CD4+/CD8+ T Lymphocyte ratio
  - CD3-CD16/56+ NK Lymphocytes (Absolute), %CD3-CD16/56+ among lymphocytes,
  - CD3-CD19+ B Lymphocytes (Absolute), %CD3-CD19+ among lymphocytes
- Anti-SARS-CoV-2 S protein RBD (Covid-19 vaccine antibody)
- Vital signs: pulse rate, systolic and diastolic blood pressure, respiratory rate, body temperature, weight.
- 12-lead single ECG (supine position): heart rate, PR interval, QRS duration, QT interval, corrected QTc (Fridericia's formula, QTcF), and RR interval. ECG assessments will be interpreted by the investigator as "Normal", "Abnormal - Not Clinically significant", "Abnormal - Clinically significant", "not evaluable", or "Not done".

For descriptive summary, data below the lower limit of quantitation/detection limit (LLOQ) will be replaced by half of the LLOQ, data above the upper limit of quantification will be replaced by upper limit of quantitation/detection limit (ULOQ) value.

### **Quantitative analyses**

For all laboratory variables, vital signs, and ECG variables above, descriptive statistics for results and changes from baseline will be provided for each scheduled visit (including the last value on-treatment) during the on-treatment period ([Section 3.1](#)). These analyses will be performed using central measurements only for laboratory variables.

For selected laboratory parameters, mean change (or percent change) from baseline may be plotted over time.

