5.2. Exclusion Criteria

Participants will be excluded from the study if any of the following criteria are met:

1. Participants with secondary ITP
2. Pregnant or lactating women
3. Electrocardiogram (ECG) findings for participants:
 - Aged ≥ 10 and < 16 years: QTcF > 449 msec (males) or > 457 msec (females)
 - Aged ≥ 16 and < 18 years: QTcF > 450 msec (males) or > 460 msec (females)
 - Aged ≥ 18 years, of QTcF > 450 msec (males) or > 470 msec (females), poorly controlled atrial fibrillation (ie, symptomatic participants or a ventricular rate above 100 beats/min on ECG), or other clinically significant abnormalities
4. History (within 5 years of Study Day 1) or current, active malignancy requiring or likely to require chemotherapeutic or surgical treatment during the study, with the exception of non-melanoma skin cancer
5. Transfusion with blood, blood products, plasmapheresis, or use of any other rescue medications with intent to increase platelet count within 14 days before Study Day 1

6. Change in CS and/or TPO-RA dose within 14 days prior to Study Day 1 (more than 10% variation from current doses)
7. Immunosuppressant drugs other than CSs within 5 times the elimination half-life of the drug or 14 days of Study Day 1, whichever is longer
8. Treatment with rituximab or splenectomy within the 3 months prior to Study Day 1
 - Participants treated with rituximab will have normal B-cell counts prior to enrollment
9. Ongoing need for the use of proton pump inhibitor drugs such as omeprazole and esomeprazole (it is acceptable to change participant to H2 receptor blocking drugs prior to Study Day 1)
10. Use of known strong-to-moderate inducers or inhibitors of CYP3A within 14 days or 5 half-lives (whichever is longer) of Study Day 1 and until the end of the active treatment period
11. Planned or concomitant use of any anticoagulants and platelet aggregation inhibiting drugs such as aspirin (except for low dose aspirin up to 100 mg per day), nonsteroidal anti-inflammatory drugs, and/or thienopyridines within 14 days of Study Day 1 and until the end of the active treatment period
12. Has received any investigational drug within the 30 days before receiving the first dose of study medication, or at least 5 times elimination half-life of the drug (whichever is longer); participant should not be using an investigational device at the time of dosing

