7.9.9. Vaccine IgG (optional)

To explore possible effects on vaccine response, Investigators will be encouraged to request injectable vaccination plans in line with age-appropriate local medical practice or guidelines from participants who have entered the study and completed at least 6 weeks of rilzabrutinib or placebo at the time of scheduled vaccination. Participants may receive vaccines for influenza, COVID-19, and tetanus (alone or in combination). Live attenuated vaccines are excluded.

Participants scheduled to receive any of the aforementioned vaccines, especially a COVID-19 vaccine, during the study periods may volunteer, after documenting informed consent, to provide

2 blood samples for vaccine-specific IgG in serum. The first blood sample should be collected within 6 weeks prior to each vaccine dose regimen and the second blood sample should be collected within approximately 3 to 6 weeks after the vaccine dose regimen is complete. Whenever possible, blood for vaccine-specific IgG should be collected at a scheduled visit; but may also be collected during an Unscheduled Visit. The collection of samples for the optional IgG assessment is applicable to both the blinded and open-label periods (See the SoA). Dates of vaccination, disease, brand name of vaccine product and antigenic strain should be recorded in the eCRF. Additional details are provided in the Laboratory Manual. See [Appendix 10](#) for country-specific requirements.

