#### *General considerations for efficacy analyses*

The statistical tests will be two-sided tests at a nominal 5% significance level for primary efficacy endpoint and key secondary efficacy endpoints.

Primary and secondary efficacy analyses will be performed in the ITT population, unless otherwise specified. The analyses of primary and key secondary endpoints are to compare the rilzabrutinib treatment group and the placebo treatment group.

The study primary and key secondary efficacy analyses will be based on the adult population at the time when the last adult participant has completed the 24-week blinded treatment period. The results based on the adults at the early analysis will be considered as final and serve as the basis

for registration application submissions. A separate analysis for the pediatric population will be similarly performed after pediatric participants have completed the blinded treatment period which may be at the same or different time when the adults have completed the blinded treatment period. The efficacy analyses on the pediatric population will be descriptive. Final analysis will be performed at the completion of the study. Additional analyses (eg, OL and LTE parts) may be performed before the final analysis. Please refer to [Section 3.8](#) for more details.

The randomization stratification factors will include splenectomy status (yes, no) and severity of thrombocytopenia (platelet counts  $<15,000/\mu\text{L}$ ,  $\geq 15,000/\mu\text{L}$ ).

For platelet count, a scheduled measurement will be used if it is available. Otherwise, an unscheduled measurement will be allocated to a scheduled visit if it is within the analysis window of the scheduled visit (see details in [Section 5.4](#)).

Rescue medications are recorded in eCRF by the investigator. Per protocol, rescue medications include IVIg, high-dose CSs, platelet infusion, and anti-D immunoglobulin infusion intended to increase platelet counts or prevent bleeding when platelet counts are less than  $20,000/\mu\text{L}$ , or for bleeding or wet purpura. Other rescue medications are not permitted.

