3. Discontinuation of study intervention before Week 13 due to reasons other than the aforementioned: data at Week 13 during the double-blind on-treatment period will be included in the analysis. Post-treatment data will be considered missing (hypothetical strategy).

Note, per protocol the end of study visit is performed at 4-week post-dose follow up where participants will have their final assessment.

**Missing data** will be handled as followed,

- A multiple imputation approach will be used to impute missing Week 13 value, using all data during the double-blind on-treatment period up to Week 13 from participants who did not take rescue medication (after 8 weeks of double-blind treatment), nor discontinued before Week 13 due to related AE or lack of response, assuming missing at random and multivariate normal distribution. The imputation model will include treatment group, randomization stratification factors, geographic region ([Section 3.1](#)) as classified variables and baseline item score as a covariate. In case the baseline score is missing for a participant, the pooled mean of baseline score will be used.

Note: before multiple imputation, data will be set to missing for 4 weeks after the use of rescue therapy.

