Note: different corticosteroids as one therapy; immunoglobulin, immunoglobulin G human and immunoglobulin human normal as one therapy; and different TPO-RAs (eg, eltrombopag and eltrombopag olamine) as one therapy; prior splenectomy as 1 therapy

- Number of prior unique ITP therapy (by WHO-DD standardized medication name): as quantitative variable and by category (1-2, 3-4,  $\geq 5$ )

Note: different corticosteroids as one therapy; prior splenectomy as 1 therapy

- Number of prior ITP therapy (by record identifier): as quantitative variable and by category (1-2, 3-4,  $\geq 5$ )

Note: prior splenectomy as 1 therapy

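### SAP 3.6.3.1 summarizes IgG, IgG1, IgG4 and anti-SARS-CoV-2 antibody with no explicit rule for samples taken after IVIg, although IVIg is permitted rescue

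*SAP*

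**What the plan says.** SAP 3.1 (General considerations for efficacy analyses) records that "Per protocol, rescue medications include IVIg, high-dose CSs, platelet infusion, and anti-D immunoglobulin infusion". The notes on prior ITP therapy in SAP Appendix 3 group "immunoglobulin, immunoglobulin G human and immunoglobulin human normal as one therapy", so one rescue option is the substance that the IgG assay measures.

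SAP 3.6.3.1 carries the entry "Immunoglobulin Levels: immunoglobulin G (IgG), immunoglobulin G Subclass 1 (IgG1" and goes on to IgG4, IgM and IgE. It separately lists anti-SARS-CoV-2 RBD antibody. For these variables the Quantitative analyses paragraph says: "For all laboratory variables, vital signs, and ECG variables above, descriptive statistics for results and changes from baseline will be provided for each scheduled visit". It adds the last on-treatment value and states no condition about rescue. Where no abnormality criterion is defined, counts against the normal range use the worst of all measurements, also without a rescue condition.

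SAP 3.1 (Observation period) bounds the double-blind on-treatment period by dosing dates alone. Baseline for non-platelet variables is the most recent value before the first dose.

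Elsewhere the SAP does deal with rescue carry-over. Platelet-week and time-to-response endpoints count the 4 weeks after rescue as no response. For ITP-PAQ Item 10, "before multiple imputation, data will be set to missing for 4 weeks after the use of rescue therapy", and IBLS follows the same approach.

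Protocol 5.2, criterion 5, excludes "use of any other rescue medications with intent to increase platelet count within 14 days before Study Day 1". Protocol 7.9.9 adds optional paired samples "To explore possible effects on vaccine response".

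**The concern.** Change in immunoglobulin levels is an exploratory endpoint for a drug that inhibits B-cell activation, and Protocol 2.7.1 lists serious infection as an important potential risk. A reader will use these tables to judge whether rilzabrutinib lowers IgG. A sample taken after IVIg measures the participant's own IgG plus what was infused.

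Rescue is compared between arms as a key secondary endpoint, so unequal IVIg use is plausible. More IVIg on placebo would raise placebo IgG and look like a fall on rilzabrutinib. IVIg on rilzabrutinib would hide a real fall. Equal use would leave the between-arm difference alone but lift both means, which could hide a fall within each arm. In the normal-range counts, an infusion before a scheduled sample could keep a low value from being seen, although a low value recorded before IVIg is still counted.

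**Working it through.** No figure in the plan bears on this point, so there is nothing to reproduce. The check sets the passages side by side and then illustrates size with assumed inputs.

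**Which samples are exposed.** Protocol 4.1.2 and 4.1.3 schedule immunoglobulins at Weeks 1, 5 and 13, then Weeks 25, 29, 33, 41 and 53, and at End of Study. In the long-term extension only End of Study is sampled. None is collected in China (Protocol Appendix 10.5). Everyone in the open-label period receives rilzabrutinib, so the randomized comparison is exposed at Weeks 5, 13 and 25 only.

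**Do post-IVIg values enter?** Under SAP 3.1 the on-treatment period ends with dosing or with the first open-label dose, not with rescue. Under 3.6.3.1 all values in that period are summarized. On that section alone, they enter.

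**Does Table 2 footnote a keep them out?** It says secondary and exploratory endpoints outside the table follow a similar strategy by endpoint type. For the continuous endpoints in the table, values are set to missing for 4 weeks after rescue, with worst-observation carry-forward when rescue comes after 8 weeks. Against applying this to IgG:
- 3.6.3.1 covers all its laboratory variables and does not cite the footnote.
- SAP 3.4.2, which carries the main-endpoint methods over, speaks of exploratory efficacy endpoints, whereas immunoglobulins sit in the safety section.
- No direction is defined for the worst IgG value.
- The footnote does not address IVIg before Day 1.

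Two programmers could reasonably produce different tables.

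**Baseline.** Immunoglobulins are not among the screening tests (Protocol 4.1.1), so the Week 1 sample is the only baseline. The washout is 14 days and the SAP's own carry-over interval is 28 days. IVIg between those limits is allowed and can raise baseline.

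**Between-arm shift (assumed inputs).** Let q be the share of sampled participants carrying infused IgG and D the mean residual infused IgG. The spurious rilzabrutinib-minus-placebo difference is (q_ril − q_pbo) × D. With D assumed at 2 to 8 g/L:

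| q_ril vs q_pbo | Difference | In g/L |
|---|---|---|
| 5% vs 10% | −0.05 D | −0.1 to −0.4 |
| 5% vs 20% | −0.15 D | −0.3 to −1.2 |
| 10% vs 30% | −0.20 D | −0.4 to −1.6 |
| 15% vs 40% | −0.25 D | −0.5 to −2.0 |
| 20% vs 20% | 0 | 0 |

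In the last row each arm's mean still rises by 0.20 D, that is 0.4 to 1.6 g/L. If IVIg were more common on rilzabrutinib, the sign would reverse.

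**Persistence (assumed half-life h, first-order decline).** The fraction left after t days is 2^(−t/h):

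| h (days) | Day 15 | Day 28 | Day 56 | Day 84 |
|---|---|---|---|---|
| 14 | 0.48 | 0.25 | 0.06 | 0.02 |
| 21 | 0.61 | 0.40 | 0.16 | 0.06 |
| 28 | 0.69 | 0.50 | 0.25 | 0.13 |
| 35 | 0.74 | 0.57 | 0.33 | 0.19 |

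IVIg given 15 days before Day 1 would leave 48% to 74% in the baseline sample. A 4-week exclusion would leave 25% to 57%, so the interval chosen for platelets and questionnaires reduces contamination by IgG without removing it.

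**The case against.** The strongest reply is that the SAP already has a rule. Immunoglobulin change is a listed exploratory endpoint, footnote a sends such endpoints to the strategy for their type, and for continuous endpoints that means 4 weeks set to missing. This stands to the extent that the SAP is ambiguous rather than plainly silent. It does not settle the matter, for the reasons given in the working.

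Other replies also limit the point:
- Pre-study IVIg precedes randomization, so it is balanced between arms in expectation and affects only within-arm readings. This stands.
- The vaccine part is small. Samples are optional pairs, the only vaccine antibody in the SAP list is anti-RBD, at least 6 weeks of treatment should precede vaccination, and COVID-19 vaccine is barred in the last 12 blinded weeks. That donor antibody registers in this assay is an assumption from outside the documents.
- IVIg is one of four rescue options, and no rate by arm is given. Participants rescued after 8 weeks may leave the blinded period after Week 12, so one pair of shares cannot serve Weeks 5, 13 and 25 alike.
- Infections are analyzed directly and rescue medication is tabulated, so IVIg use can be read beside IgG. This helps, but it does not separate infused from own IgG in the means.
- Dropping post-IVIg values alone would remove data after randomization, possibly unevenly by arm. This stands, and it is why the all-values table should remain.

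**Conclusion.** The point holds in limited form. Section 3.6.3.1 has no IVIg rule for IgG, IgG1, IgG4 and anti-RBD antibody, the on-treatment period includes post-IVIg samples, and the reach of Table 2 footnote a is unclear. The tables can therefore mimic or mask a drug-related change at Weeks 5, 13 and 25, and an IVIg-raised baseline can distort within-arm change. The size cannot be derived from the documents. The 0 to 2.0 g/L range rests wholly on assumed IVIg shares and residual IgG.

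A reader might infer more than the documents support:
- That every visit is contaminated. Sampling is sparse.
- That baseline IVIg biases the comparison of arms. Randomization balances it in expectation.
- That IVIg would turn vaccine non-responders into responders. The SAP defines no vaccine-responder analysis.
- That efficacy conclusions are at risk. These summaries are descriptive and untested, and the primary and key secondary endpoints do not use them.

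**What to change.** In SAP 3.6.3.1:

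1. Keep the summary of all values.
2. Add a summary of IgG, IgG1, IgG4 and anti-RBD antibody, with normal-range counts where applicable, that excludes values after any IVIg for a stated window justified by how long infused IgG persists: at least 4 weeks, with a longer 8- or 12-week version.
3. Flag participants with IVIg in the same window before Day 1, or exclude them from change from baseline in that summary.
4. Flag vaccine sample pairs with IVIg between the samples or shortly before them.
5. Report the number of excluded values by arm and visit.
6. Reconcile 3.6.3.1 with Table 2 footnote a, and state that the footnote's implied worst-observation imputation does not apply to laboratory endpoints.

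The cost is SAP wording, a derived flag and some extra tables. Rescue is already recorded in the eCRF and prior IVIg is already tabulated, so no new collection and no change to rescue or eligibility rules is needed. The supplementary summary will hold fewer values, possibly unevenly by arm, which is why the all-values table stays and the exclusions are counted.

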### **Analyses according to PCSA**

Potentially clinically significant abnormality (PCSA) analyses will be performed based on the PCSA list currently in effect at Sanofi at the time of the database lock ([Section 5.6](#)). For parameters for which no PCSA criteria are defined, similar analyses will be done using the normal range, if applicable. For parameters defined as efficacy endpoints, PCSA summaries will not be provided.

Analyses according to PCSA will be performed based on the worst value during the treatment-emergent period, using all measurements (either local or central, either scheduled, nonscheduled or repeated).

For laboratory variables, vital signs, and ECG variables above, the incidence of participants with at least one PCSA during the treatment-emergent period will be summarized regardless of the baseline level and according to the following baseline status categories:

- Normal/missing
- Abnormal according to PCSA criterion or criteria

For ECG, the incidence of participants with at least one abnormal ECG during the treatment-emergent period will be summarized regardless of the baseline level and according to the following baseline status categories:

- Normal/Not evaluable/Not done
- Abnormal - Not Clinically significant
- Abnormal - Clinically significant

#### ***Additional analyses for drug-induced liver injury***

The following additional analyses will be performed for drug-induced liver injury:

- Time to onset of the initial ALT or AST elevation ( $>3 \times \text{ULN}$ ) and total bilirubin elevation ( $>2 \times \text{ULN}$ ) (time to first observation of ALT or AST elevation or total bilirubin elevation, whichever comes first) during the treatment-emergent period will be analyzed using Kaplan-Meier method.
- A graph of the distribution of peak values of ALT versus peak values of total bilirubin during the treatment-emergent period will be provided.
- For each liver function test (eg, ALT), participants having experienced a PCSA (eg, ALT  $>5 \text{ ULN}$ ) will be summarized using the following categories (for each treatment period or cumulatively as appropriate): Returned to baseline PCSA status (or returned to value  $\leq \text{ULN}$  in case of missing baseline) before last IMP dose, Returned to baseline PCSA status after last IMP dose, Never returned to baseline PCSA status (or not yet returned to baseline PCSA status at the data cutoff if applicable), No assessment after elevation. This summary will be performed by categories of elevation (ALT  $>3$ ,  $>5$ ,  $>10$ ,  $>20 \text{ ULN}$ ).

